#### 6.1 EFFICACY ASSESSMENTS

Tumor response will be assessed at the Pre-Study Visit, Day 1 of odd-numbered cycles, and at the follow-up visit using Response Evaluation Criteria In Solid Tumors (RECIST v1.1) from Eisenhauer et al. (2009), presented in Appendix A of the protocol, and further described below in Appendix B. In general, target lesions will be assessed as Complete Response (CR), Partial Response (PR), Stable Disease (SD), or Progressive Disease (PD) and non-target lesions will be assessed as Complete Response (CR), Incomplete Response/Stable Disease (SD), or Progressive Disease (PD). Tumor responses from target lesions and from non-target lesions will be used to determine Overall Response as described in Appendix B. If the Overall Response is CR or PR, tumor assessments are to be repeated within 4 weeks. Overall Response will be tabulated by cycle and treatment; the responses for target lesions and non-target lesions will be included in listings, but will not be tabulated. If Overall Response of PD is observed at any time, the patient will not automatically be discontinued. Further imaging or target lesion measurements will not be required and all other trial visits and procedures will continue.

If assessments are made after the Overall Response of PD is recorded, then the Overall Response at all subsequent cycles will be PD and will be included at every cycle for which the Overall Response is recorded through Cycle 11 (see Section 7.2).

#### **6.1.1** TIME TO EVENT ENDPOINTS

The primary efficacy endpoint is Overall Survival (OS), the time from Baseline to death due to any cause, calculated as date of death- date of Cycle 1 Day 1+1. Secondary time-to-event endpoints are:

- TTP: the time from Baseline to the first Overall Response of PD, calculated as date of first PD date of Cycle 1 Day 1+1, and
- PFS: the time from Baseline to the first Overall Response of PD or death due to any cause if the subject dies without experiencing PD, calculated as date of first PD or death date of Cycle 1 Day 1+1.

#### **6.1.2** TUMOR RESPONSE

The secondary endpoints which are based directly on tumor response are:

- ORR (OR Rate): proportion of subjects who have CR or PR,
- DCR (DC Rate): proportion of subjects who have CR, PR, or SD, and
- Best Overall Response during the duration of the study.
   (The best overall response for each subject is the best response recorded from the start of the study treatment until the end of study, in the order of CR, PR, SD, or PD from best to worst.)

#### **6.1.3** EXPLORATORY EFFICACY

Laboratory parameters associated with hepatic dysfunction and cirrhosis (ALT, AST, bilirubin, and albumin levels, prothrombin time (PT), and International Normalized Ratio (INR)) will be assessed every cycle and will be considered exploratory efficacy variables.

The effect of CF102 on  $\alpha$ -fetoprotein (alpha-fetoprotein; AFP) will be assessed. AFP levels will be assessed at Baseline and on Day 1 of each subsequent cycle.

Liver chemistry tests and viral load will be presented as exploratory efficacy variables, as will WBC A3AR expression. Viral load for Hepatitis B Virus (HBV) and Hepatitis C Virus (HCV) will be assessed at Baseline, at Day 1 of each subsequent odd cycle, at the end of dosing, and at the Follow-up visit for subjects with positive serology at Screening.

#### **6.2 SAFETY EVALUATIONS**

Safety parameters assessed throughout the trial include adverse events, ECOG performance status, vital signs, weight, physical examinations, laboratory parameters including thyroid functions, ECG, and concomitant medications. Any clinically significant change from baseline in a laboratory parameter will be reported as an AE. Liver chemistry tests and viral load will be presented as exploratory efficacy variables.

At each visit, all AEs will be recorded in the appropriate section of the CRF and will be evaluated by the Investigator. The minimum information required for each AE includes the following:

- Type of event
- Duration (start and end dates)
- Severity
- Seriousness
- Relationship to study drug (Unrelated, Possibly Related, Probably Related, or Related)
- Action taken
- Outcome.

In most cases, the CTCAE v4.0 criteria will preferably be used to grade severity; however, if an AE is not listed in the CTCAE, the following grading scale may be used: Mild (Grade 1), Moderate (Grade 2), Severe (Grade 3), Life-Threatening (Grade 4), or Fatal (Grade 5).

#### 7. STATISTICAL CONSIDERATIONS AND DATA ANALYSIS

Tables and data listings will be prepared using SAS Version 9.0 or higher. A subject's Baseline value for a specified variable will be the measurement for that variable taken on Day 1 of Cycle 1, unless the pre-study assessment was performed within 3 days prior to baseline. In the latter case, assessments do not need to be repeated prior to initiation of dosing for Physical Examination, Body Weight, Clinical Laboratory testing, Pregnancy Test, and ECOG PS, as noted in the Schedule of Procedures in Section 5 and the Baseline value will be the value at Screening.

For any variable with Change From Baseline (CFB) calculated, CFB will be calculated as CFB = Value at Post-Baseline visit – Value at Baseline.

If the final pre-treatment assessment was performed at Screening, prior to Baseline, then CFB is defined as the difference between the value at the post-Baseline visit and the value at Screening.

Simple descriptive statistics for continuous data are: n (number of non-missing observations), mean, standard deviation, maximum, median, and minimum. Categorical data will be summarized by the number and percentage of subjects in each category. The data will be summarized upon completion of the final subject. All data collected for the OL period will be listed and select variables will be summarized. Listings and summaries for the OL period will be presented separately and a separate SAP will be prepared. The following pertains to the analyses and summaries for the DB period.

#### 7.1 ANALYSIS POPULATIONS

Analyses will be conducted using the populations described below.

The **Safety Population** consists of all subjects who received at least one dose of study medication. Analyses of safety assessments will be performed using the Safety Population.

The **Intent-To-Treat (ITT) Population** is defined as all subjects in the Safety Population with any post-Baseline assessment recorded. Exclusion of subjects from the ITT Population will be determined prior to unblinding. All efficacy analyses will be performed using the ITT Population.

The **Per Protocol (PP) Population** is defined as all subjects in the ITT Population with no major protocol deviations, including major violations of inclusion and exclusion criteria and violation of RECIST requirements regarding the number of target lesions at Screening (Appendix B). Exclusion of subjects from the PP Population will be determined prior to unblinding. Tumor response (Sections 6.1.2 and 7.6.4) will be analyzed for the PP Population.

#### 7.2 GENERAL ANALYSIS

The following standards will be applied for analyses unless otherwise specified. Simple descriptive statistics for continuous data are: n (number of non-missing observations), mean, standard deviation, maximum, median, and minimum. Categorical data will be summarized by the number and percentage of subjects in each category. Summaries of efficacy variables will be presented by visit through end of Cycle 11. Best Overall Response will be summarized once for the entire study. All data will be listed for the Safety Population, sorted by investigator number, subject number and, where appropriate, by visit, including data from visits after Cycle 11. The choice of Cycle 11 as the final time for tabulation will be finalized prior to unblinding. Tumor assessments performed at the EOS Visit, the Follow-up Visit, and Unscheduled Visits will be assigned to the next cycle and will be analyzed with that cycle. Tumor responses recorded on the CRF will be listed. Other data from Unscheduled Visits will not be summarized, except for AEs.

#### 7.3 SUBJECT DISPOSITION

The total number of subjects will be presented with the number and percentage of subjects in each analysis population by treatment and overall. The number and percentage of subjects who completed the study, who discontinued, and primary reason for discontinuation will be summarized by treatment for the Safety Population.

#### 7.4.2 HCC DISEASE HISTORY AND PRIOR THERAPIES

HCC disease history includes

- date of initial HCC diagnosis and staging,
- date of most recent relapse and/or re-staging,
- method used for diagnosis (histology / cytology or American Association for the Study of Liver Diseases (AASLD) Practice Guideline algorithm),
- history of viral hepatitis, including date of diagnosis,
- hepatitis B and hepatitis C virus serology (positive or negative), with the last date of testing, and
- known complication(s) of cirrhosis and/or portal hypertension.

History of viral hepatitis is recorded as "Yes, Hepatitis B"; "Yes, Hepatitis C"; "No"; or "Not known", with the date of diagnosis recorded for the first two responses, both of which are possible. The summary statistics will include the counts and percentages for each of the four possible responses by treatment for the Safety Population.

Known complication(s) of cirrhosis and/or portal hypertension are reported on the CRF as "Ascites", "Esophageal varices with bleeding", or "Other (specify)". If none of these responses are selected, then the response should be reported as "None".

Prior therapies include

- modality,
- start and stop dates of treatments,
- numbers of cycles, and
- best response to each treatment.

The number of subjects reporting the use of a modality at least once will be summarized by treatment for the Safety Population. Other variables pertaining to HCC disease history and prior therapies will be listed for the Safety Population.

A table of the number of target hepatic lesions and the number of target non-hepatic lesions (Appendix B) at Screening for the Safety Population will be presented.

A table of the incidence of Extrahepatic Spread (EHS), Portal Vein Thrombosis (PVT) at Baseline, including either EHS or PVT ("Yes" or "No"), will be provided.

#### 7.4.3 MEDICAL HISTORY

Medical history, excluding past HCC, cirrhosis, and viral hepatitis-related history, will be summarized using frequencies and percentages of subjects with a finding or procedure for each body system (or "None") by treatment for the Safety Population by treatment and overall. "Other" will be listed but will not be included in the summaries.

#### 7.5 MEDICATION AND TREATMENT ANALYSIS

#### 7.5.1 COMPLIANCE AND EXPOSURE

Compliance will be calculated as the number of total capsules dispensed (over the duration of the study) minus the total number of capsules returned, and then that quantity is divided by twice the duration of treatment in days. The duration of treatment is date of final dose minus date of Baseline + 1. If the date of final dose is missing or if the subject is still receiving treatment, the date of final dose will be imputed as described in Section 8. Descriptive statistics for compliance and the duration of treatment will be provided for the Safety Population by treatment. The summary statistics pooled across treatments will also be computed for duration of treatment, to be used in efficacy evaluations as described in Sections 7.6.1-7.6.3.

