8.2 Dose Modification

Any safety-related modification of study drug dosing (i.e., dose reduction or interruption of scheduled dosing) and the reason for such action must be clearly noted on the Adverse Events page of the CRF, and the Medical Monitor informed.

In the case of any Grade 3 toxicity by CTCAE v4.0 judged by the Principal Investigator to be at least “possibly” drug-related, the dose of study drug will be interrupted for up to 7 days. If toxicity does not resolve to Grade \leq 1 within 7 days, the subject will be discontinued from treatment. If toxicity does resolve to Grade \leq 1 within 7 days, dosing will be resumed at the decreased dose of 1 capsule per day.

In the case of any Grade 4 toxicity judged by the Principal Investigator to be at least “possibly” drug-related, the dose of study drug will be withdrawn permanently.

Only 1 dose reduction will be allowed. If a Grade 3 or 4 toxicity judged by the Principal Investigator to be at least “possibly” drug-related occurs upon rechallenge at the reduced dose, study drug dosing will be withdrawn permanently.

All changes in dosing will be recorded on the CRF.

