8.6 Treatment Compliance

Bottles of study drug dispensed to subjects at the start of each treatment cycle will contain a sufficient supply of CF102 or matching placebo for 28 days of continuous dosing (1 cycle). Treatment compliance will be monitored by the investigative site staff at each clinic visit.

Bottles of study drug dispensed to subjects at the start of each treatment OL cycle will contain a sufficient supply of CF102 for 28 days of continuous dosing (1 cycle). Treatment compliance will be monitored by the investigative site staff at each clinic visit.

The Investigator will instruct subjects to bring all partially used and empty pill bottles to each clinic visit. Any dosing error will be reported to the Investigator and Sponsor's monitor.

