#### 8. MISSING DATA

Missing dates will be imputed only when the date is required to calculate the duration of an event for summary. As such, the only missing date that would need to be imputed is the date of final dose, required for calculation of duration of treatment. In such situations, the month and year would be recorded. For subjects who have completed dosing, the missing date of final dose will be imputed as the 15-th of the month; for subjects who are still receiving treatment, the missing date of final dose will be imputed as the date of the last completed visit.

Missing data from intermediate visits for AFP, WBC A3AR, viral load, and laboratory assessments when considered exploratory efficacy variables will be imputed using Last Observation Carried Forward (LOCF). Missing data for the latter laboratory variables will not be imputed when examined with laboratory assessments as safety variables. Due to the nature of the study, there is no imputation due to discontinuation.

The protocol specifies that certain assessments will not be repeated at Baseline (Cycle 1 Day 1) if assessed at the Pre-Study visit <= 3 days prior to Cycle 1 Day 1, resulting in missing values for Baseline; in such cases, the missing value at Baseline will be imputed by the value from the Pre-Study visit.

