Study Drug Accountability and Treatment Compliance

Site/ Subject	Treatment	Total Number of Capsules Dispensed	Total Number of Capsules Returned	Date of Final Dose (1)	Date of Baseline Visit	Treatment Duration (Days)	Compliance (%)
xxx/xxxxx	XXXXX	XXX	XXX	DD/MM/YY	DD/MM/YY	XXX	XX.X
xxx/xxxxx	XXXXX	XXX	XXX	DD/MM/YY	DD/MM/YY	XXX	XX.X

The numbers of capsules dispensed and returned by visit are in the next listing.

Programming Notes: Treatment Duration= date of final dose minus date of Baseline + 1.

Compliance (%) =100\*(total number of capsules dispensed over study - total number of capsules returned over study)/ (2\*treatment duration). Total number of capsules dispensed over study = 65\*sum of the Number of Bottles Dispensed from next listing.

Total number of capsules returned over study = 65\*sum of the Number of Unopened Bottles Returned from above table

+ sum of Number of capsules returned (open bottle) from next listing.

 Date of Last Recorded Visit for subjects who are ongoing.

Listing 16.2.4.2
Study Drug Accountability by Visit

Site/ Subject	Treatment	Visit	Date	Treatment Number	Number of Bottles Dispensed	Comments	Number of unopened bottles returned	Number of capsules returned (open bottle)	Comments
xxx/xxxxx	XXXXX	Cycle 1	xx/xxx/xxxxx	XXXX	XXX	XXXXXX			
		Cycle 2	xx/xxx/xxxxx	XXXX	XXX	XXXXXX	XXX	XXX	XXXXXXX
		Cycle 3	xx/xxx/xxxxx	XXXX	XXX	XXXXX	XXX	XXX	XXXXXXX
xxx/xxxxx	XXXXX	Cycle 1	xx/xxx/xxxxx	XXXX	XXX	XXXXXX			
		Cycle 2	xx/xxx/xxxxx	XXXX	XXX	XXXXX	XXX	XXX	XXXXXXX
		Cycle 3	xx/xxx/xxxxx	XXXX	XXX	XXXXXX	XXX	XXX	XXXXXXX
		Cycle 4	xx/xxx/xxxxx	XXXX	XXX	XXXXXX	XXX	XXX	XXXXXXXX

Programming Note: Continue for all cycles.

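### The compliance measure in SAP 7.5.1 scores adherent dose-reduced subjects below 100% and, for a separate reason, can score adherent ongoing subjects above 100%

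*SAP*

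**What the plan says.** SAP 7.5.1 defines compliance as capsules dispensed less capsules returned over the study, after which "that quantity is divided by twice the duration of treatment in days". The Table 14.1.7 footnote and the programming notes to Listing 16.2.4.1 repeat the divisor. None of the three has a term for a reduced dose or an interruption.

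The length of treatment comes from the same section: "The duration of treatment is date of final dose minus date of Baseline + 1". For subjects still on treatment, SAP section 8 states that "the missing date of final dose will be imputed as the date of the last completed visit", and the footnote to Listing 16.2.4.1 says much the same.

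The notes to Listing 16.2.4.1 fix the bottle size: "Total number of capsules dispensed over study = 65\*sum of the Number of Bottles Dispensed". Protocol 8.6 says that the bottles given at the start of each cycle "will contain a sufficient supply of CF102 or matching placebo for 28 days of continuous dosing (1 cycle". It does not say how many bottles that is.

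Protocol 8.2 and SAP 2.4 direct an interruption of at most 7 days after a possibly related Grade 3 toxicity. If it resolves in that time, "dosing will be resumed at the decreased dose of 1 capsule per day".

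SAP section 9 says that interruptions and reductions were not specifically recorded and refers the reader to the action taken for each adverse event. The action codes in Listing 16.2.7 include drug delayed and drug discontinued, but have no entry for drug reduced.

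**The concern.** A compliance rate should show how far subjects took what they were told to take. With a fixed divisor of two per day, a subject who obeys an instruction to stop for a week and then take one capsule daily looks the same as a subject who misses doses. Table 14.1.7 reports the rate by arm. If protocol-directed reductions are more frequent in one arm, a difference in tolerability would appear there as a difference in adherence.

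This matters somewhat more because the shells contain no dose-reduction table, although Protocol 12.4.1 calls for dose reductions to be summarised. The compliance figure may be the only tabulated trace of them.

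The ongoing subjects raise a different problem, in the opposite direction. Capsules that have been handed over but not yet taken enter the numerator, while the days on which they would be taken are left out of the divisor.

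**Working it through.** The documents give no compliance value to reproduce, so the check applies the SAP formula to subjects who are fully adherent by construction.

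**Inputs**
- C = 100 × (dispensed − returned) / (2 × D), with D the treatment duration in days (SAP 7.5.1).
- 65 capsules per bottle (Listing 16.2.4.1 notes).
- 2 capsules a day at full dose, so 56 per 28-day cycle; 1 a day after a reduction; 0 to 7 days off before it (Protocol 8.2, SAP 2.4).
- Assumptions: one bottle per cycle, so 9 spare capsules come back each cycle, and all bottles before the last are fully reconciled.

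**Check on a full-dose subject who has finished.** After k cycles, C = 100 × (65k − 9k) / (2 × 28k) = 100%. The formula is right for this subject.

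**Dose-reduced subject.** With a days at full dose, h days off and 1 capsule a day for the rest, C = 100 × (2a + D − a − h) / (2D).

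| a | D | h = 0 | h = 7 |
|---|---|---|---|
| 7 | 84 | 91/168 = 54.2% | 84/168 = 50.0% |
| 28 | 56 | 84/112 = 75.0% | 77/112 = 68.8% |
| 28 | 112 | 140/224 = 62.5% | 133/224 = 59.4% |
| 28 | 308 | 336/616 = 54.5% | 329/616 = 53.4% |
| 84 | 112 | 196/224 = 87.5% | 189/224 = 84.4% |

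With h = 0 this is 50% + 50% × a/D, so 50% is a limit, and a score of 55% or less needs D of at least 10 × a. An almost immediate reduction with 7 days off can fall slightly lower (a = 0, D = 56: 49/112 = 43.8%).

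**Ongoing subject at full dose.** Take the last completed visit as Day 1 of cycle k+1, with a bottle dispensed that day. Then D = 28k + 1 and C = 100 × (65(k+1) − 9k) / (2(28k+1)).
- Cycle 3 Day 1: (195 − 18)/114 = 177/114 = 155.3%
- Cycle 6 Day 1: (390 − 45)/282 = 345/282 = 122.3%
- Cycle 7 Day 1: (455 − 54)/338 = 401/338 = 118.6%
- Cycle 12 Day 1: (780 − 99)/618 = 681/618 = 110.2%

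The numerator equals 2D + 63, so the excess over 100% is 63/(2D). It passes 20 points only when D is below 63/0.4 = 157.5 days. If the last completed visit is Day 15, the same numerator is divided by 2(28k+15): 177/142 = 124.6% in cycle 3 and 233/198 = 117.7% in cycle 4.

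**After the change**
- Dose-reduced subject with 28 full-dose days, 7 off and 77 reduced: 133 capsules taken against 133 prescribed = 100%, instead of 59.4%.
- Ongoing subject at Cycle 3 Day 1, counting only the two reconciled bottles and their 56 days: 112/112 = 100%, instead of 155.3%.

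**The case against.** The case for leaving the plan alone has four parts.

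- *The measure is disclosed and has a recognisable meaning.* Capsules taken over the full planned dose resembles a dose-intensity measure, and the table footnote prints the formula. This stands as far as it goes: the main fault is that the result is called compliance.
- *Ongoing subjects are few and long-treated.* With about 78 subjects and 75 deaths, about 3 would survive, if those counts are met. Subjects still on blinded drug by then are likely to be far into treatment, where the score is roughly 105 to 119%. Three subjects at 110% in an arm of 52 (78 × 2/3) would move the mean by about 3 × 10/52 = 0.6 points. If the last blinded bottle is counted at the switch to open label, the excess vanishes. All of this stands.
- *The data for a full correction may not exist.* Reductions were not specifically recorded, the action codes have no reduced category, and returned capsules cannot tell a missed dose from a prescribed one. This also stands, and it limits the fix.
- *Nothing depends on the figure.* Compliance is descriptive, no compliance threshold defines the Per Protocol Population, and it does not enter the survival analysis. This is correct.

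These arguments shrink the point without removing it. The plan still reports by arm, as compliance, a number that falls when a subject obeys the protocol.

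**Conclusion.** The point holds and is minor. The fixed divisor scores an adherent dose-reduced subject anywhere from about 50% to nearly 100%, depending on how early the reduction comes relative to total treatment. Independently, the unreconciled last bottle pushes an adherent ongoing subject above 100%. The ongoing figures assume one 65-capsule bottle per cycle and full reconciliation of earlier bottles; more bottles per visit would raise them.

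A reader might infer more than the documents support:
- That dose-reduced subjects generally score near 50%. That is a limit for early reductions; reduction after 84 of 112 days gives 87.5%.
- That the factor of two causes the scores above 100%. It does not: two per day is correct at full dose, and the excess comes from the bottle counted beyond the end of the duration.
- That exposure is misreported. Table 14.1.7 gives exposure as days of treatment, which uses no capsule count.
- That the CF102 arm is marked down by a known amount. The documents give no reduction frequency by arm, so neither the direction nor the size of any difference between arms can be stated.

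**What to change.** 1. **Ongoing subjects.** Count only bottles whose returns are reconciled in Listing 16.2.4.2, and only the days those bottles cover. Dropping the last bottle alone leaves a small mismatch (112/114 = 98.2% at Cycle 3 Day 1), so both parts are needed.
2. **Reduced or interrupted subjects, dates known.** Use capsules prescribed as the denominator wherever the dates can be established from adverse event or accountability records: 2 per day at full dose, 0 on protocol-directed interruption days and 1 per day after reduction.
3. **Dates not known.** Relabel the measure in Table 14.1.7 as percent of full planned dose, and add a footnote that protocol-directed reductions and interruptions lower it.
4. **Consistency.** Reconcile SAP section 9, which treats the action-taken field as the source for reductions, with the Listing 16.2.7 codes, which cannot show one.

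The cost is an edit to SAP 7.5.1 and the table footnote plus some programming. The downside is that reduction dates will be incomplete, so some subjects may be covered only by the relabelled measure. Returned capsule counts alone should not be used to infer a reduction, because missed doses look the same.
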